We have initiated a proof of concept study under IND 104,917 and with local IRB approval (Evaluation of Regional Ventilation in Normal Subjects and Subjects with Airway and Lung Disorders Using 19F Magnetic Resonance Imaging of Inert Perfluorinated Gases mixed with Oxygen (PFP): A Phase 1 Study). We have consented 44 subjects minus one withdrawal, screened 43 subjects in the study with the characteristics described in Table 1 and scanned 30 subjects (reasons for non scanning of subjects: 1 voluntary withdrawal prior to any study participation, 5 body habitus (too obese), 4 screen fails, 4 MRI contraindications).

Disease Status	Number of Subjects Screened (F/M)
Normal	13 (5/8)
COPD	11(7/4)
COPD, Emphysema	4 (1/3)
COPD Emphysema, Asthma, Small Airway Disease	1(1/0)
COPD Asthma, Small Airway Disease	1 (1/0)
Asthma	2 (2/0)
Asthma, small airway Disease	2 (2/0)
Cystic Fibrosis	5 (4/1)* all with lung transplant
Lung Transplant	2 (1/1)
Small Airway Disease	1 (1/0)
Unknown Etiology	1 (0/1)
Total	43 (25/18)

Table 1: Disease profiles of screened subjects in the phase 1 proof of concept study

2 Trial Objectives

The proposed study will determine regional qualitative and quantitative lung function information in the context of the clinical trajectory of COPD defined by the cross sectional cohort components. Due to the long time-frame of this disease we are using a modified case control design that allows a cross-sectional evaluation of the proposed measures in aims 1-2 to identify putative markers that could later be tested as prognostic factors in longitudinal studies. In the case of these PFx/oxygen mixtures, the availability of multi-liter quantities allows for wash-in/wash-out image acquisition and analysis allowing direct measures of gas trapping in a manner not easily achieved with any existing modality.

3 Trial Design

The central hypothesis and current observation is that PFx gases used as contrast agents provide functional images of the lung airways including important regional ventilation information such as ventilation defect severity and gas trapping. We will test the central hypothesis and accomplish the overall objective by addressing the following specific aims:

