6.1 Statistical Methods and Subject Population for Analysis

We have three main methods to employ to characterize of clinical phenotypes using MR Imaging bases features.

One method is to estimate with reasonable precision the mean and standard deviation ventilation parameters from 19F gas imaging. So with 250 (5 groups) subjects we should be able using a t-test (or ANOVA) to detect a variation in defect volume of approximately 6% in the smallest sample (N = 26/group, GOLD III/IV) (alpha 0.05 and 90% power) and 5% in the reference groups (N=40/group). [Statmate Ver 2, GraphPad Software (La Jolla, Ca)].

Further, we wish to evaluate the diagnostic/prognostic ability of the MRI parameters to provide distinction among current ‘phenotypes’ and perhaps extend better discrimination with the MRI parameters from study aims. We will also use statistical modeling for this project to correlate the features obtained from the gas-probe MR imaging-based measures with one or more of the clinical assessment measures recorded in Aim 1.2, to better characterize disease phenotypes and identify the most promising prognostic indicators.

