In a similar context, a recent study has shown such promise for certain CT imaging-based features (7). Thus, if the role of MR imaging-based measures can be established in a similar fashion then, associated with a link f , is some MR-defined variable Z which can define a biomarker, risk factor or phenotype R , resulting in the general linkage statement of $R \leftarrow f \rightarrow \text{GOLD+MRI}$. The makeup of this biomarker would contain information obtained from one or more measures Aims 1, 1.1 and 2 as well as other clinical status information X (as codified in the GOLD score or more generally some combination of the demographic, physiological and past history information, (Aim 1.2). This biomarker would then provide a more rapid and efficient means for deciding treatment strategies. We will examine the diagnostic/phenotyping ability of the MR imaging-based features (Aims 1 and 2) in terms of their ability to predict existing clinical phenotypes (GOLD) characterized and other clinical features (Aim 1.2). For this purpose, we will divide the predictors into two categories: a) clinical assessments features ($X_{a1}, X_{a2}, \dots, X_{ak}$), obtained from existing clinical, physiologic, and HRCT imaging, measured under Specific Aims 1.1 and 1.2; b) features obtained from MR imaging ($X_{b1}, X_{b2}, \dots, X_{bl}$), identified under Aims 1 and 2. A generalized linear model of the form [1] will be fitted using the method of maximum likelihood:

$$g(Y_t) = \beta_{a0} + \beta_{a1}X_{a1} + \dots + \beta_{ak}X_{ak} + \epsilon \quad [1]$$

The predictability of this model will be calculated using the Akaike Information Criterion (AIC) statistic (2), which balances the quality of fit (likelihood) against model complexity (8). Selection of the optimal subset of predictors will be achieved via a search over predictor space to identify the subset that maximizes the AIC statistic.

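### The predictor search is told to maximise AIC with no formula given; under the standard lower-is-better AIC this selects the worst-scoring subset

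*Combined protocol and SAP*

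**What the plan says.** Section 6.1 plans a generalized linear model, fitted by maximum likelihood, that relates clinical phenotype to two groups of predictors. Group (a), the X_a terms, holds clinical, physiologic and HRCT measures. Group (b), the X_b terms, holds "features obtained from MR imaging". Earlier in the same section the modelling is said to serve to "identify the most promising prognostic indicators".

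The criterion is AIC, described only in words as a statistic "which balances the quality of fit (likelihood) against model complexity". The selection rule is one sentence: "Selection of the optimal subset of predictors will be achieved", it says, "via a search over predictor space to identify the subset that maximizes the AIC statistic".

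The documents give no formula for AIC and no sign convention, and no other section states the opposite direction. The only support is two literature references. Model [1], as printed, contains X_a terms and no X_b terms.

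**The concern.** The rule can be executed as it stands, and under the usual definition of AIC it runs backwards. A search meant to find the best compromise between fit and parsimony would return the candidate with the poorest one. This is the only subset-selection rule the plan gives for the biomarker work. Section 2 (Trial Objectives) says the study is meant "to identify putative markers that could later be tested as prognostic factors in longitudinal studies", so the output of this search is what would be carried forward.

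The candidate set is also unclear. The stated purpose is to judge what the MR features add, yet the only model printed leaves them out. A reader cannot tell from the text whether the search covers them. Both the direction and the candidate set are needed to reproduce the selection.

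**Working it through.** The plan states no figure for this rule, so there is nothing to reproduce first. The direction follows from the definition. The size has to be illustrated under assumptions.

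**1. Direction.** With log L the maximised log-likelihood and k the number of fitted parameters,

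AIC = −2 log L + 2k.

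Better fit lowers AIC and each extra parameter raises it, so the best trade-off is the minimum. Adding one predictor changes AIC by 2 − LR, where LR is its likelihood-ratio statistic:

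- Minimising AIC keeps the predictor when LR > 2.
- Maximising AIC keeps it when LR < 2, that is, when it contributes little.

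A pure noise predictor has LR approximately chi-square on 1 df, and P(LR < 2) = 0.84. The literal rule therefore retains noise predictors about 84% of the time.

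**2. Reversed sign.** log L − k = −AIC/2, so maximising log L − k is the same as minimising AIC. The printed word would be correct if that form were declared. It is not.

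**3. Approximate retention under the literal rule.**

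- From the documents: 130 COPD and 120 normal subjects (section 1.5).
- Assumed: a binary COPD/normal outcome, six independent candidate predictors, and a mean difference of d SD for each informative one.

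The signed root of LR is roughly normal with SD 1 and mean d × √(130 × 120 / 250) = d × √62.4. The literal rule keeps an informative predictor when this root lies between −1.414 and 1.414.

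| d (SD) | Mean of root | P(keep one informative predictor) | P(keep at least one of three) | P(empty model, six informative) |
|---|---|---|---|---|
| 0.7 | 5.53 | <0.001 | <0.001 | >0.99 |
| 0.5 | 3.95 | 0.006 | 0.02 | 0.97 |
| 0.3 | 2.37 | 0.170 | 1 − 0.830³ = 0.43 | 0.830⁶ = 0.33 |
| 0.15 | 1.18 | 0.586 | 1 − 0.414³ = 0.93 | 0.005 |

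**4. Simulation.** All-subsets logistic regression with the same 130/120 split, six candidates (64 subsets), 400 runs per scenario, and AUC measured on 20,000 new simulated subjects.

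| Scenario | d (SD) | New-data AUC, minimise AIC | New-data AUC, maximise AIC |
|---|---|---|---|
| 3 informative, 3 noise | 0.7 | 0.80 | 0.50 |
| 3 informative, 3 noise | 0.5 | 0.72 | 0.50 |
| 3 informative, 3 noise | 0.3 | 0.62 | 0.52 |
| 3 informative, 3 noise | 0.15 | 0.54 | 0.53 |
| 6 informative | 0.7 | 0.88 | 0.50 |
| 6 informative | 0.3 | 0.67 | 0.56 |
| 6 informative | 0.15 | 0.56 | 0.55 |

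With three informative predictors, the literal rule kept at least one in 0%, 2%, 43% and about 94% of runs from the largest effect to the smallest, close to the approximation in step 3. With six informative predictors it chose the intercept-only model in 100% of runs at 0.7 SD and 32% at 0.3 SD. Maximising log L − k chose the same subset as minimising AIC in all 2,800 runs (7 scenarios × 400).

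**5. Separate check with unequal effects.** N = 250, three true predictors with assumed log-odds 0.8, 0.6 and 0.5, three noise predictors, 100 data sets. Minimising AIC kept all three true predictors in 95 data sets. Maximising kept any of them in only 5, and its chosen subset scored on average 55.5 AIC units worse.

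**6. Continuous outcome.** Gaussian model, N = 250, three informative and three noise predictors, residual SD 1, 400 runs each. New-data R², minimising versus maximising: 0.31 versus −0.01 at coefficient 0.4, 0.08 versus −0.01 at 0.2, and about 0 for both at 0.1.

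**The case against.** The strongest reply is that the intent is plain. The section asks for a best subset, describes a criterion that penalises complexity, and cites references for it. Standard software reports the lower-is-better form, and a competent analyst would minimise it. On this view the AUC losses describe something unlikely to happen. That is a fair point about practical impact: the figures show what the literal rule would do, not an expected loss for the study. It does not rescue the text. An analyst who minimises departs from the written plan without a record, and one who follows it gets the wrong model.

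Second, the simulation is not the planned analysis. The outcome, link and number of predictors are not specified, and section 6.1 refers to GOLD phenotypes and five groups rather than a two-way split. This is correct, and the numbers are illustrative only. The direction does not depend on them.

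Third, the literal rule does not always discard useful predictors. With very weak effects it keeps most of them and little is lost. This stands.

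Fourth, model [1] may be a clinical base model to which MR terms would later be added. That is possible, but the text does not say so. The section defines both predictor groups and aims at a combined GOLD and MRI marker, so the MR features have to enter the search in some declared way.

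Finally, the aims in section 3.1 and the t-test/ANOVA statement do not rely on this rule. This is also right, and it limits the reach of the point.

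**Conclusion.** The concern holds. As written, and under the standard definition of AIC, the only stated selection rule picks the worst-scoring subset and contradicts its own purpose. That conclusion needs no assumption about effect size. It would be reversed only if a higher-is-better form such as log L − k were declared.

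The practical size is conditional. If the rule were followed literally, discrimination would fall to about chance for features separating the groups by 0.5 SD or more, fall in part at 0.3 SD, and hardly change at 0.15 SD. These figures rest on an assumed binary outcome, six independent candidates and assumed effects at N = 250. The modelling is exploratory and the error is probably one of wording, so this should be fixed but does not threaten the study.

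**What to change.** In section 6.1:

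- Replace maximising with minimising, and state AIC = −2 log L + 2k. Equivalently, state that log L − k is maximised.
- Add one sentence saying that the search covers the MR features X_b as well as the X_a terms printed in model [1], and whether the clinical terms are searched jointly with them or held in as a base model.

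The cost is one word, one formula and one sentence, with no new data and no change to sample size.

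Separately and optionally, report the selected model's AUC or deviance from cross-validation or bootstrap, with the search repeated in each resample. This costs only computing time and would make the reported accuracy somewhat less favourable. In the simulation with three informative and three noise predictors under minimum AIC, apparent versus new-data AUC was 0.81 versus 0.80 at 0.7 SD, 0.66 versus 0.62 at 0.3 SD and 0.59 versus 0.54 at 0.15 SD.

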6.2 Termination Criteria

Premature termination of this clinical trial may occur because of a regulatory authority decision, change in opinion of the IRB, or at the discretion of the FDA. DUMC also reserves the right to discontinue the trial prior to inclusion of the intended number of subjects, but intends only to exercise this right for valid scientific or administrative reasons.

After such a decision, the investigator must contact all participating subjects within 4 weeks. All trial materials must be collected and all CRFs completed to the greatest extent possible.

7 Direct Access to Source Data/Documentation

During trial conduct, DIAL will conduct periodic monitoring to ensure that the protocol and GCP are being followed. DIAL staff will review source documents to confirm that the data recorded on CRFs is accurate. The investigator and institution will allow DIAL staff and appropriate regulatory authorities direct access to source documents to perform this verification.

8 Quality Control and Quality Assurance

The trial site (Duke) may be subject to review by IRB and/or to quality assurance audits performed by Duke, and/or to inspection by appropriate regulatory authorities from the US. It is important that the investigator(s) and their relevant personnel are available during these monitoring visits and possible audits or inspections and that sufficient time is devoted to the process.

9 Ethical Considerations

9.1 Institutional Review Board

It is the responsibility of the investigator to obtain prospective approval of the trial protocol, protocol amendments, informed consent forms, and other relevant documents, e.g., advertisements, if applicable, from the IRB. All correspondence with the IRB should be retained in the Investigator file. Copies of IRB approvals should be retained at Duke.

The only circumstance in which an amendment may be initiated prior to IRB approval is where the change is necessary to eliminate apparent immediate hazards to the subjects consistent with applicable regulations. In that event, the investigator must notify the IRB in writing in a time frame consistent with Duke policy and applicable regulations.

9.2 Ethical Conduct of the Trial

The trial will be performed in accordance with the protocol, ICH, GCP guidelines, and applicable local regulatory requirements and federal laws.

9.3 Subject Information and Consent

The informed consent form must be approved by the Duke IRB and must be in compliance with ICH, GCP, local regulatory requirements, and federal laws. The investigator must ensure that each trial subject is fully informed about the nature and objectives of the trial and possible risks associated with participation. The investigator will obtain written informed consent from

each subject's before any study-specific activity is performed. The informed consent form used in this trial, and any changes made during the course of the trial, must be prospectively approved by the IRB before use. Additionally, the FDA will be notified of any changes prior to implementation as appropriate. The investigator will retain a copy of each subject's signed consent form.

The subjects will be asked to provide contact information for their primary care (or other physician) so that they can be notified if any potentially clinically relevant findings are obtained from standard clinical procedure (e.g HRCT or PFT's). This contact information will be kept in the subjects research record.

10 Data Handling and Record Keeping

As used in this protocol, the term CRF should be understood to refer to either a paper form or an electronic data record or both, depending on the data collection method used in this trial. A CRF is required and should be completed for each included subject. The completed original CRFs are the sole property of Duke and should not be made available in any form to third parties, except for authorized representatives of Duke or appropriate regulatory authorities, without written permission from Duke.

It is the investigator's responsibility to ensure completion and to review and approve all CRFs. CRFs must be electronic signed by the investigator or by an authorized staff member. These signatures serve to attest that the information contained on the CRFs is true. At all times, the investigator has final personal responsibility for the accuracy and authenticity of all clinical and laboratory data entered on the CRFs.

The CRFs, the MR and HRCT images and PFTs testing results will serve as source documents for this study.

10.1 Data Management

All patient data will be collected on a dedicated and encrypted Duke University server. The data entry system will check for out-of-range and other implausible data entries and immediately prompt the study coordinator to confirm or correct the entry. All patient data files will be de-identified.

10.2 Data Storage

All MRI images are stored in DIAL for QA/QC and image analysis; CAMRD will be notified of cases of unacceptable image quality to enable the rescheduling of scans accordingly. Subjects can be rescanned a maximum of one (1) time. The data will be de-identified and stored in the research image management system SQUID, a research image management system in DIAL.

